7.2.2. Exclusion Criteria

A patient who meets any of the following criteria will be excluded from the study:

1. Background pharmacologic LMT, nutraceuticals or over-the-counter (OTC) therapies known to affect lipids, at a dose/regimen that has not been stable for at least 4 weeks (8 weeks for PCSK9 inhibitors) before the screening visit and patient is unwilling to enter the run-in period
2. For patients entering Part A, unable to temporarily discontinue apheresis from the baseline visit through the week 4 visit
3. Receiving lipid apheresis, a setting (if applicable) and schedule that has not been stable for approximately 8 weeks before the screening visit or an apheresis schedule that is not anticipated to be stable over the duration of the treatment period (48 weeks). A stable schedule is defined as a weekly (every 7 ± 1 days) or every other week (every 14 ± 2 days) schedule
4. Plasmapheresis within 8 weeks of the screening visit, or plans to undergo plasmapheresis during Part A or Part B
5. Presence of any clinically significant uncontrolled endocrine disease known to influence serum lipids or lipoproteins
6. Newly diagnosed (within 3 months prior to randomization visit [week 0/day 1]) diabetes mellitus or poorly controlled (hemoglobin A1c [HbA1c] >9%) diabetes

7. Chronic use of systemic corticosteroids, unless used as replacement therapy for pituitary/adrenal disease with a stable regimen for at least 6 weeks prior to randomization
Note: topical, intra-articular, nasal, inhaled and ophthalmic steroid therapies are not considered as 'systemic' and are allowed
8. History of a myocardial infarction (MI), percutaneous coronary intervention (PCI), uncontrolled cardiac arrhythmia, carotid surgery or stenting, stroke, transient ischemic attack (TIA), valve replacement surgery, carotid revascularization, endovascular procedure or surgical intervention for peripheral vascular disease within 3 months prior to the screening visit
9. History of cancer within the past 5 years
10. Use of any active investigational drugs within 1 month or 5 half-lives, whichever is longer
11. Conditions/situations such as:
 - a. Any clinically significant abnormality identified at the time of screening that, in the judgment of the investigator or any sub-investigator, would preclude safe completion of the study or constrain endpoints assessment; eg, major systemic diseases, patients with short life expectancy

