 - b. Considered by the investigator or any sub-investigator as inappropriate for this study for any reason, eg:
 - Deemed unable to meet specific protocol requirements, such as scheduled visits
 - Investigator or any sub-investigator, pharmacist, study coordinator, other study staff or relative thereof directly involved in the conduct of the protocol, etc.
 - Presence of any other conditions (eg, geographic or social), either actual or anticipated, that the investigator feels would restrict or limit the patient's participation for the duration of the study
12. Laboratory findings during screening period (not including randomization labs):
 - Positive urine pregnancy test in females of childbearing potential
 - Triglycerides >300 mg/dL (>4.52 mmol/L) (1 repeat lab is allowed)
 - Alanine aminotransferase (ALT) or aspartate aminotransferase (AST) >3 x upper limit of normal (ULN) (1 repeat lab is allowed)
 - CPK >3 x ULN (1 repeat lab is allowed)
13. Known hypersensitivity to monoclonal antibodies or any excipient in the evinacumab solution for infusion
14. Sexually active males, and sexually active females of childbearing potential at screening
15. Female patients who have commenced menstruating at any time during the study and are either:
 - Found to have a positive urine pregnancy test, or

- Sexually active, not using or not willing to use an established highly effective contraception method prior to subsequent dosing of study treatment, during the study, and for at least 24 weeks after the last dose of study drug. Highly effective contraceptive measures include:
 - Stable use of combined (estrogen- and progestogen-containing) hormonal contraception associated with inhibition of ovulation initiated 2 or more menstrual cycles prior to screening: oral, intravaginal, transdermal
 - Stable use of progestogen-only hormonal contraception associated with inhibition of ovulation initiated 2 or more menstrual cycles prior to screening: oral, injectable, implantable
 - Intrauterine device or intrauterine hormone-releasing system
 - Bilateral tubal ligation
 - Vasectomized partner. Note: vasectomized partner is a highly effective birth control method provided that the partner is the sole sexual partner of the WOCBP trial participant and that the vasectomized partner has received medical assessment of the surgical success

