Future Biomedical Research Plasma ¹²			X				X						X				X
Other																	
Review of Diet, compliance with LMT		X	X	X	X	X	X	X	X	X	X	X	X	X	X	X	X
Carotid Ultrasound Imaging ¹³							X						X				

9.1.1. Footnotes for the Schedule of Events Table**9.1.1.1. Table 1 Schedule of Events – Part A, PK and PD Portion**

1. Study assessments are to be performed and blood samples are to be collected before the dose of study drug in all patients.
2. ECG should be performed before blood samples are collected at visits requiring blood draws.
3. All laboratory samples should be collected before administration of study drug.
4. Sex hormones include luteinizing hormone, FSH, estradiol, and total testosterone.
5. Pregnancy test with a local urine pregnancy test should be done on sexually active females who have experienced menarche and are of childbearing potential.
6. Including assay of total ANGPTL3. Extra samples may be used to assess the concentration of concomitant medications, eg, statins.
7. The PK sample should be drawn predose and at the end of the IV infusion on days when study drug is administered
8. If apheresis is administered on a dosing day, it is preferred to administer apheresis before the evinacumab infusion. The PK sample should be collected prior to apheresis and at the end of the evinacumab infusion. In the event apheresis is administered after evinacumab administration, the PK sample should be collected prior to and at the end of evinacumab infusion, prior to apheresis.
9. The ADA sample should be drawn before study drug administration.
10. Parent or legal guardian must sign a separate informed consent form (ICF) and patient must sign a separate informed assent prior to collection of Future Biomedical Research samples. Patients are still eligible to enroll in the study if they do not wish to participate in the Future Biomedical Research.
11. Parent or legal guardian must sign a separate informed consent form (ICF) and patient must sign a separate informed assent to participate in the optional genomics sub-study prior to collection of whole blood DNA samples. Patients are still eligible to enroll in the study if they do not wish to participate in the genomics sub-study
12. Carotid ultrasound imaging will be performed only at sites with this capability. Every effort should be made for patients to undergo 2 carotid ultrasound imaging assessments before the first dose of study drug. The assessments should be separated by at least 1 day.

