13. For patients who require stabilization of their background LMT (including apheresis) or need to undergo genotyping to confirm diagnosis of HoFH.
14. If the patient requires a run-in the ICF should be signed at that time; otherwise ICF should be signed at screening visit.
15. On dosing days, vital signs consisting of blood pressure and pulse rate will also be collected pre-dose and 30 minutes and 60 minutes after completion of the IV infusion
16. For patients who do not enter Part C, there will be an 8-week follow-up period (visit 12).

17. If continuing to Part C, this visit can occur on the same day as visit 1 of Part C.

9.1.1.2. Table 2 Schedule of Events – Part B, 48-Week Efficacy and Safety Portion

1. Study assessments are to be performed and blood samples are to be collected before the dose of study drug in all patients. For patients undergoing apheresis: Study assessments are to be performed and blood samples are to be collected before the apheresis procedure; every effort should be made to administer study drug within 1 day of the apheresis procedure.
2. On dosing days, vital signs consisting of blood pressure and pulse rate will also be collected pre-dose and 30 minutes and 60 minutes after completion of the IV infusion
3. ECG should be performed before blood samples are collected at visits requiring blood draws.
4. All laboratory samples should be collected before administration of study drug.
5. Sex hormones include luteinizing hormone, follicle stimulating hormone, estradiol, and total testosterone.
6. Pregnancy test with a local urine pregnancy test should be done on sexually active females of childbearing potential.
7. Including assay of total ANGPTL3. Extra samples may be used to assess the concentration of concomitant medications, eg, statins.
8. The PK sample should be collected predose and at the end of the IV infusion on days when study drug is administered.
9. For patients who are not undergoing apheresis, the PK sample should be drawn before the administration of study drug. For patients undergoing apheresis, a PK sample should be collected immediately before the apheresis procedure if it is performed before the evinacumab infusion.
10. For patients who are not undergoing apheresis, the ADA sample should be drawn before study drug administration. For patients undergoing apheresis, the ADA sample should be drawn before the apheresis procedure if it is performed before the evinacumab infusion.

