14. At weeks 8 and 16 of the follow-up period all patients will be contacted by phone to query LMT compliance, to inquire about AEs or changes to concomitant medications, confirm required contraception use, and remind patients of pregnancy reporting. Sexually active females of childbearing potential will report the results of their home pregnancy test. For patients who decide to enter a compassionate use or early access program, the EOT visit will be their last visit and they will forgo the 24-week follow-up period.
15. Overlapping assessments completed at the EOT visit of Part A or Part B do not need to be duplicated during visit 1 of Part C. Part C visit 1 should occur on the same day as Part A visit 11 or Part B visit 11. All necessary assessments are listed in the applicable SOE (Part A or Part B) column for visit 11.
16. Patient can only receive the dose once all assessments from Part A or Part B Visit 11 are completed.
17. For patients who decide to enter a CUP or EAP, the EOT visit will be their last visit and they will forgo the 24-week follow-up period.

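### The pregnancy-test footnotes direct a test only in sexually active girls and are not aligned with exclusions 12 and 15: a minor, low-cost safety correction

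*Protocol*

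**What the plan says.** **Who is to be tested.**
- Part A (Protocol 9.1.1.1, Table 1 footnote 5): the test "should be done on sexually active females who have experienced menarche and are of childbearing potential".
- Part B (Protocol 9.1.1.2, Table 2 footnote 6): "Pregnancy test with a local urine pregnancy test should be done on sexually active females of childbearing potential". Part C (9.1.1.3, Table 3 footnote 7) uses the same words.
- Part C follow-up phone contacts (Table 3 footnote 14): "Sexually active females of childbearing potential will report the results of their home pregnancy test".
- SAP 10.7 repeats the first three footnotes. Protocol 9.2.3.5 lists the urine test, names no other pregnancy test, sets no population of its own and refers back to Tables 1 to 3.

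**Which results matter (Protocol 7.2.2).**
- Exclusion 12: "Positive urine pregnancy test in females of childbearing potential". Its heading limits it to "Laboratory findings during screening period (not including randomization labs", and exclusion 6 places the randomization visit at week 0/day 1.
- Exclusion 14: "Sexually active males, and sexually active females of childbearing potential at screening".
- Exclusion 15: "Female patients who have commenced menstruating at any time during the study and are either" found to have a positive urine test, or sexually active without highly effective contraception. The two arms are alternatives.

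**What follows from a pregnancy.** Study drug stops permanently (Protocol 8.4.2.1), the sponsor is told within 24 hours of identification (10.1.4), and the SAP counts it as an event of special interest (4.8.1.2).

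**The concern.** The rules that act on a positive test cover more girls than the footnotes that say whom to test. Stopping drug and reporting both depend on the pregnancy being recognised, and the urine test is the only pregnancy test scheduled.

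A girl known to be sexually active is covered twice: the footnotes direct a test, and exclusion 15 requires contraception. Both safeguards rest on the same knowledge. The remaining case is a post-menarchal girl whose sexual activity is undisclosed or unrecognised. She has neither a directed test nor a contraception requirement, so an early pregnancy could go undetected while dosing continues. What is at stake is individual safety. The LDL-C analysis is untouched.

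**Working it through.** There is no planned figure to reproduce. The check sets the texts side by side and counts the marked visits.

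**Step 1. Screening.** The footnotes name sexually active females of childbearing potential. Exclusion 14 already removes those girls. At screening, then, the footnotes direct a test only in girls who are ineligible anyway. Exclusion 12 implies a screening test in every female of childbearing potential but does not state it as a procedure.

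**Step 2. Day 1 onward.** Exclusion 12 has ended. Exclusion 15 presupposes a test result in any girl who has started menstruating, but names no test and no visit. The footnotes reach her only if she is identified as sexually active. Tables 1 to 3 have no row for menarche or sexual activity. Tanner stage is scheduled at 4 points up to Part C week 48 (screening, visit 11 of Part A or B, Part C visits 7 and 13) and is recorded as a stage from 1 to 5.

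**Step 3. Marked tests after screening, up to Part C week 48.** Inputs are the Urine Pregnancy Test and Administer Study Drug rows of protocol Tables 1 to 3, as they appear in the text.

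| Segment | Visits marked | Marks | On dosing days |
|---|---|---|---|
| Part B (Table 2) | 2, 4, 7, 8, 9, 10, 11 | 7 | 6 (not visit 4) |
| Part A, entering Part C (Table 1) | 2, 6, 8, 10, 11 | 5 | 2 (visits 2 and 11) |
| Part C (Table 3) | 2 to 13 | 12 | 12 |

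- By way of Part B: 7 + 12 = 19 marks, of which 6 + 12 = 18 fall on dosing days.
- By way of Part A: 5 + 12 = 17 marks, of which 2 + 12 = 14 fall on dosing days.

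Visit 11 counts as a dosing day because Table 3 footnote 15 puts Part C visit 1 on the same day. The counts include the week 48 dose marked in Table 3. If the last dose is at week 44, the dosing-day counts become 18 − 1 = 17 and 14 − 1 = 13. The 3 follow-up marks (visits 14 to 16, two of them phone contacts) are left out.

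**Step 4. A mismatch in Part B.** Protocol Table 2 marks the test at visit 4 (week 2, no dose) and not at visit 5 (week 4, dose). The SAP copy marks visit 5 and not visit 4. The total is 7 either way. Under the protocol table the week 4 dose has no test marked. The tables were read by a program, so this needs confirming against the source.

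**Step 5. Plausible age.** Patients are 5 to 11 years old at screening. By way of Part B, 2 + 24 + 48 = 74 weeks, or 1.42 years, so a child aged 11 (11.0 to 12.0) is about 12.4 to 13.4 at Part C week 48. By way of Part A, 2 + 16 + 48 = 66 weeks, or 1.26 years, giving 12.3 to 13.3. Menarche on study is therefore foreseeable.

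**The case against.** The strongest reply is that the limit is a deliberate, risk-based choice. It is the same in all three parts, the children are 5 to 11 at screening, and a girl who is truly not sexually active is not at risk. Exclusion 15 can act on a positive result however obtained. If exclusion 12 implies a screening test, exclusion 15 can be said to imply on-study testing too. Unscheduled visits are allowed for any warranted reason (Protocol 9.1.3). Sex hormones are scheduled, Part C follow-up calls remind all patients about pregnancy reporting, and exclusions 15 and 16 cannot be applied on study without asking about sexual activity.

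Much of this stands, and it keeps the point small. But none of these provisions directs an on-study test in a post-menarchal girl not identified as sexually active. Where a criterion implies a test and the footnote on that very row names a narrower group, a site will follow the footnote.

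Three stronger readings are tempting and are not supported:
- A reader might infer that the protocol bars testing other girls. It does not. The footnotes say who should be tested and do not forbid more.
- A reader might take all 19 or 17 marks as missing pre-dose tests. Only 18 and 14 fall on dosing days, and for a girl who reaches menarche on study only the later visits count.
- A reader might infer that undetected pregnancies are likely. The documents give no number of post-menarchal girls, and the girl at risk must also be sexually active without its being known.

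**Conclusion.** The point holds as a misalignment of wording: the footnotes are narrower than exclusion 12 and than the positive-test arm of exclusion 15, and no visible text closes the gap after screening. For a girl already past menarche at screening and not identified as sexually active, it covers 19 marked tests by way of Part B (18 on dosing days) or 17 by way of Part A (14 on dosing days).

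The practical risk is very small. About 20 patients are planned (6 + 14), each in Part A or Part B but not both. Few girls, possibly none, would be affected, and efficacy is not. Severity is minor: a low-cost safety alignment.

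This rests on the visible text. Part of Protocol 3.3 (Risk-Benefit) and the case report form were not available, and menarche or sexual activity may be recorded on the form.

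**What to change.** Reword Table 1 footnote 5, Table 2 footnote 6, Table 3 footnote 7 and the home-test sentence in Table 3 footnote 14 to: 'urine pregnancy test in all females who have reached menarche, at every visit marked, before dosing on dosing days'. Ask about menarche at those visits. Change the SAP copies for consistency only.

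In the same amendment, confirm whether the Part B mark belongs at visit 4 or visit 5, and place it at visit 5. Without that, the new wording would still leave the week 4 dose without a test.

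Cost: no added visits. Per girl past menarche there are at most 19 extra urine tests up to Part C week 48, plus 3 in follow-up (2 at home), or none in follow-up if she forgoes it for compassionate use or early access. Urinalysis is already scheduled at 11 of the 19 marked visits (Part B visits 2, 7, 8, 9, 11; Part C visits 3, 5, 7, 9, 11, 13). Because the change widens who undergoes a procedure, it needs IRB/EC approval of the amendment (Protocol Section 14) and a review of the consent form (13.2).

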9.1.1.3. Table 3 Schedule of Events – Part C

1. Study assessments are to be performed and blood samples are to be collected before the dose of study drug in all patients. For patients undergoing apheresis: Study assessments are to be performed and blood samples are to be collected before the apheresis procedure; every effort should be made to administer study drug within 1 day of the apheresis procedure.
2. On dosing days, vital signs consisting of blood pressure and pulse rate will also be collected pre-dose and 30 minutes and 60 minutes after completion of the IV infusion
3. ECG should be performed before blood samples are collected at visits requiring blood draws.
4. Assessment of Tanner Stage, sex hormones, and post-baseline height only applicable to patients < 18 years old.
5. All laboratory samples should be collected before administration of study drug.
6. Sex hormones include luteinizing hormone, follicle stimulating hormone, estradiol, and total testosterone.
7. Pregnancy test with a local urine pregnancy test should be done on sexually active females of childbearing potential.
8. Including assay of total ANGPTL3. Extra samples may be used to assess the concentration of concomitant medications, eg, statins.
9. The PK sample should be collected predose and at the end of the IV infusion on days when study drug is administered.
10. For patients who are not undergoing apheresis, the PK sample should be drawn before the dose of study drug. For patients undergoing apheresis, a PK sample should be collected immediately before the apheresis procedure if it is performed before the evinacumab infusion.
11. For patients who are not undergoing apheresis, the ADA sample should be drawn before study drug administration. For patients undergoing apheresis, the ADA sample should be drawn immediately before the apheresis procedure if it is performed before the evinacumab infusion.

12. Parent or legal guardian must sign a separate informed consent form (ICF) and patient must sign a separate informed assent prior to collection of Future Biomedical Research samples. Patients are still eligible to enroll in the study if they do not wish to participate in the Future Biomedical Research
13. Carotid ultrasound imaging will be performed only at sites with this capability. The assessment should be performed approximately every 6 months at every other Visit F.
14. At weeks 8 and 16 of the follow-up period all patients will be contacted by phone to query LMT compliance, to inquire about AEs or changes to concomitant medications, confirm required contraception use, and remind patients of pregnancy reporting. Sexually active females of childbearing potential will report the results of their home pregnancy test. For patients who decide to enter a compassionate use or early access program, the EOT visit will be their last visit and they will forgo the 24-week follow-up period.
15. Overlapping assessments completed at the EOT visit of Part A or Part B do not need to be duplicated during visit 1 of Part C. Part C visit 1 should occur on the same day as Part A visit 11 or Part B visit 11. All necessary assessments are listed in the applicable SOE (Part A or Part B) column for visit 11.
16. Patient can only receive the dose once all assessments from Part A or Part B Visit 11 are completed.
17. For patients who decide to enter a CUP or EAP, the EOT visit will be their last visit and they will forgo the 24-week follow-up period.

9.1.2. Early Termination Visit

For patients in Part A who are withdrawn from the study early, an ET should occur as soon as possible with assessments normally planned at the Part A, EOT visit.

For patients in Part B who permanently discontinue study drug before week 24, an ET visit should occur as soon as possible with assessments normally planned at the Part B, EOT visit (week 24).

For patients in Part C who permanently discontinue study drug before the week 48 visit, an ET visit should occur as soon as possible with assessments normally planned at the Part C, EOT visit (week 48).

If the patient agrees to continue in the study, after completing the ET visit, the patient should resume the original study schedule (except for study treatment administration) until the EOS. Specifically, for patients in Part B, all efforts should be made to perform the week 24 assessments (regardless of study treatment administration).

If the patient does not agree to continue in the study after completing the ET visit, patients should enter the follow-up period and be followed for at least 24 weeks from the last dose of study drug, and a final end of study visit can take place with assessments as specified in the end of study visit.

If a patient enters a CUP or EAP, they may forgo the 24-week follow-up period.

9.1.3. **Unscheduled Visits**

All attempts should be made to keep patients on the study schedule. Unscheduled visits may be necessary to repeat testing following abnormal laboratory results, for follow-up of AEs, or for any other reason, as warranted.

9.2. **Study Procedures**

9.2.1. **Procedures Performed Only at the Screening/Baseline Visit**

The following procedures will be performed for the sole purpose of determining study eligibility or characterizing the baseline population: Demographics, medical/surgical history, medication history, and thyroid-stimulating hormone (TSH).

9.2.2. **Efficacy Procedures**

All laboratory samples will be collected before the dose of study drug is administered.

Blood samples for lipid panels should be collected in the morning, in fasting conditions (ie, overnight, at least 8 hours fast, only water) for all clinic visits. Intense physical exercise within 24 hours, preceding blood sampling is discouraged.

Total-C, HDL-C, Apo B, Apo A-1, TG, and Lp(a) will be directly measured by the central laboratory. LDL-C will be calculated using the Friedewald formula. If TG values exceed 400 mg/dL (4.52 mmol/L) or if calculated LDL-C values are below 25 mg/dL (0.65 mmol/L), LDL-C will be measured via the beta quantification method (rather than via the Friedewald formula). Non-HDL-C will be calculated by subtracting HDL-C from the TC.

Detailed procedures of sample preparation, storage, and shipment are provided in the laboratory manual.

9.2.2.1. **Lipid Panel**

Fasting (at least 8 hours) blood samples will be collected at specified time points shown in Section 9.1 for assessment of the lipid profile, comprising calculated LDL-C, HDL-C, non-HDL C, TC, and TGs. These samples will also be used for specialty lipid panel assessment when it is scheduled at the same time as the lipid panel assessment.

9.2.2.2. **Specialty Lipid Panel**

Fasting (at least 8 hours) blood samples will be collected at specified time points shown in Section 9.1 for assessment of the specialty lipid profile, comprising Apo B, Apo A-1, ratio of Apo B/Apo A-1, ApoCIII, ApoE, and Lp(a). The specialty lipid panels will be assessed in the same sample that is collected for the lipid panel.

9.2.3. **Safety Procedures**

9.2.3.1. **Vital Signs**

Vital signs, including temperature, sitting blood pressure, pulse, and respiration rate, will be collected predose at time points according to [Table 1](#), [Table 2](#), and [Table 3](#).

On dosing days, vital signs consisting of blood pressure and pulse rate will also be collected pre-dose and 30 minutes and 60 minutes after completion of the IV infusion.

Blood pressure should be measured in the same arm throughout the study after the patient has been resting quietly for at least 5 minutes. Pulse rate will be measured at the time of the measurement of blood pressure.

